5.0 TREATMENT PROGRAM

5.1 Overview of Treatment Plan

Day 1	Day 15	Day 28
VX15/2503 IV	VX15/2503 IV	End of Cycle/Evaluation

VX15/2503 will be administered intravenously over 60 minutes on Days 1 and 15 of a 28 day cycle. Patients should be monitored for signs and symptoms of infusion reactions during the drug infusion and for 4 hours after completion of post-infusion flush (e.g., monitor vital signs every 15 minutes during VX15/2503 infusion and every 30 minutes thereafter). Precautions for anaphylaxis should be observed during VX15/2503 administration. Emergency resuscitation equipment and medications should be present for immediate use in the immediate area where patients are receiving their infusions. If a patient develops a \geq Grade 2 infusion related reaction, the infusion should be stopped and standard institutional guidelines for management of infusion reactions should be followed. Note: If the initial dose is well tolerated subsequent doses will required patients to be monitored for 1 hour after completion of post-infusion flush.

See Section [6.2.3](#) for management and dose modification guidelines for infusion related reactions. If there is no evidence of an infusion related reaction during the initial 2 infusions of VX15/2503, then no observation period is required for subsequent treatment cycles. In the event an infusion related reaction occurs thereafter, the four-hour observation period should be reinstated.

A cycle of therapy is considered to be 28 days. A cycle may be repeated for a total of 13 cycles, up to a total duration of therapy of approximately 12 months. As some of the correlatives require same-day shipping (see [Section 8.5](#)), caution should be paid to the day of the week therapy should start and drug infusion should occur so that correlative samples are able to be sent out for analysis without delay.

Drug doses should be adjusted based on weight measured within 7 days prior to the beginning of each cycle.

Update: With the release of Amendment #2A, the dose confirmation portion of the study is complete. Given this, Part B will be open to patients \geq 12 months and \leq 30 years of age with relapsed and refractory osteosarcoma once the initial 6 adult patients complete toxicity assessments per [Section 11.6](#).

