8.0 EVALUATIONS/MATERIAL AND DATA TO BE ACCESSIONED

8.1 Required Clinical, Laboratory and Disease Evaluation

All clinical and laboratory studies to determine eligibility must be performed within 7 days prior to enrollment unless otherwise indicated. Laboratory values used to assess eligibility (see [Section 4.0](#)) must be no older than seven (7) days at the start of therapy. Laboratory tests need **not** be repeated if therapy starts **within** seven (7) days of obtaining labs to assess eligibility. If a post-enrollment lab value is outside the limits of eligibility, or laboratory values are older than 7 days, then the following laboratory evaluations must be re-checked within 48 hours prior to initiating therapy: CBC with differential, bilirubin, ALT (SGPT) and serum creatinine. If the recheck is outside the limits of eligibility, the patient may not receive protocol therapy and will be considered off protocol therapy. Imaging studies, bone marrow aspirate and/or biopsy, must be obtained within 14 days prior to start of protocol therapy (repeat the tumor imaging if necessary).

STUDIES TO BE OBTAINED	Pre-Study	During Cycle 1	Prior to Subsequent Cycles [^]
History	X	Weekly	X
Physical Exam with vital signs ¹²	X	Weekly	X
Height, weight, BSA	X		X
Performance Status	X		
CBC, differential, platelets	X	Twice Weekly (every 3 to 4 days) ³	Every subsequent cycle on D1 ⁴ and D15 ⁴
Pharmacokinetics ¹	X	X	X
Urinalysis	X		
Electrolytes including Ca ⁺⁺ , PO ₄ , Mg ⁺⁺	X	Weekly	X
Creatinine, ALT, bilirubin	X	Weekly	X
Albumin	X		X
Tumor Disease Evaluation	X	End of Cycle 1	Every other cycle x 2 then q 3 cycles ⁵
Tumor Disease Evaluation- Part B Phase 2	X		After cycles 2,4 and 6 and then q 3 cycles ⁵
Bone Marrow Evaluation ⁷	X	End of Cycle 1 ⁸	Every other cycle x 2 then q 3 cycles ⁸
Pregnancy Test ²	X	With tumor disease	With tumor disease

THIS PROTOCOL IS FOR RESEARCH PURPOSES ONLY, SEE PAGE 1 FOR USAGE POLICY

		evaluation ²	evaluation ²
Oxygen Saturation ⁶	X		
Immunogenicity Study	X	X ⁹	X ⁹
T Lymphocyte Saturation	X	X ¹⁰	X ¹⁰
Total Soluble SEMA4D	X	X ¹¹	X ¹¹
Tumor Tissue	X ¹³	X ¹⁴	X ¹⁴

- [^] Studies may be obtained within 72 hours prior to the start of the subsequent cycle.
- ¹ See [Section 8.3](#) for timing of PK studies.

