- ² Women of childbearing potential require a negative pregnancy test prior to starting treatment; sexually active patients must use an acceptable method of birth control for the duration of the study. Abstinence is an acceptable method of birth control. Pregnancy testing is required prior to tumor imaging per institutional guidelines.
- ³ If patients have Grade 4 neutropenia then CBCs should be checked at least every other day until recovery to Grade 3 or until meeting the criteria for dose limiting toxicity.
- ⁴ If patients develop Grade 4 neutropenia then CBCs should be checked every 3 to 4 days until recovery to Grade 3
- ⁵ Tumor Disease Evaluation should be obtained on the next consecutive cycle after initial documentation of either a PR or CR. Subsequent scans may restart 2 cycles after the confirmatory scan. Please note that for solid tumor patients, if the institutional investigator determines that the patient has progressed based on clinical or laboratory evidence, he/she may opt not to confirm this finding radiographically.
- ⁶ Only if there is clinical indication of inadequate pulmonary function. See [Section 4.1.7.4](#).
- ⁷ Patients with known bone marrow disease should have baseline bone marrow evaluation
- ⁸ If bone marrow evaluation pre-study is positive for metastatic disease
- ⁹ Immunogenicity Study see [section 8.4](#) for timing of Immunogenicity studies
- ¹⁰ T Lymphocyte Saturation see [section 8.5](#) for timing of T Lymphocyte Saturation studies
- ¹¹ Total Soluble SEMA4D Solubility Assay see [section 8.6](#) for timing of SEMA4D solubility studies.
- ¹² Monitor vital signs every 15 minutes during VX15/2503 infusion and every 30 minutes thereafter for 4 hours.
- ¹³ Tumor tissue should be obtained if available. If a patient does not have tissue available, the study chair must be notified prior to enrollment. See [Section 8.7](#).
- ¹⁴ In the event a subject requires a biopsy for surgery and tumor tissue is removed, tumor tissue will be requested for analysis. Tumor biopsies will not be performed solely for research purposes. See [Section 8.7](#).

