11.0 STATISTICAL AND ETHICAL CONSIDERATIONS

11.1 Sample Size and Study Duration

A minimum of 4 evaluable patients will be required for Part A. The expected maximum number of evaluable patients required to complete part A is 12. Once the MTD or recommended Phase 2 dose has been defined, up to 6 additional patients with recurrent or refractory solid tumors without restrictions on heme evaluability may be enrolled to acquire PK data in a representative number of young patients (i.e. patients < 12 years old). Therefore, the maximum number of patients anticipated to be enrolled into Part A is 23 patients which allows for 6 patients at each of 2 dose levels, 6 additional patients for PK, and 20% inevaluability. Review of the enrollment rate into previous COG new agent studies indicates that 4 patients per month are expected. Therefore, the study is expected to be completed within about 6 months. In the unlikely event that both dose levels are expanded to 12 patients due to DLTs of different classes, the absolute maximum number of patients enrolled into Part A would be 38. The absolute maximum would be expected to be completed within 10 months.

Additionally once the MTD/or RP2D has been determined in Part A, the Phase 2 portion of the study (Part B) will use a Simon's optimal two-stage design. In the first stage, 19 disease control and RECIST response evaluable patients will be enrolled. Each patient will be evaluated for both outcome measures: (1) disease control success; and (2) RECIST response (CR or PR v. not CR or PR). The decision rule for the two stage study design is summarized in [Section 11.6](#). A maximum of 37 patients are expected to be enrolled to allow for 20% inevaluability. This is expected to be completed within about 10 months. Overall, a maximum of 60 patients are expected to be enrolled into the study, and this should be completed within about 16 months. An absolute maximum of 75 patients would take up to 19 months to complete enrollment.

Strata:

- a) Part A-Determination of the MTD
- b) Part B- Osteosarcoma Phase 2 cohort.

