11.6 Study Design - Part B

Data collected from patients from the dose determining portion (Part A) treated at the MTD/RP2D and who meet eligibility criteria for Part B of the study will be counted in the Phase 2 evaluation. The following Simon's optimal two stage design will be used in each stratum.

The two stage design is illustrated below:

Stage	Number of patients enrolled in stage	Cumulative response results	Decision
1	19	4 or fewer disease control successes and 1 or fewer RECIST responders	Terminate the trial with the conclusion that VX15/2503 is not associated with sufficient activity for further investigation
		5 or more disease control success or 2 or more RECIST responders	Continue to stage 2

THIS PROTOCOL IS FOR RESEARCH PURPOSES ONLY, SEE PAGE 1 FOR USAGE POLICY

2	10	8 or fewer disease control successes and 4 or fewer RECIST responders	Terminate the trial with the conclusion that VX15/2503 is not associated with sufficient activity for further investigation
		9 or more disease control successes or 5 or more RECIST responders	Terminate the trial with the conclusion that VX15/2503 is associated with sufficient activity for further investigation

Part B will be initially opened to 6 adult patients. The Rolling 6 design logic will be applied for assessing toxicity in the initial cohort of 6 adults. If 2 or more patients in this cohort experience a DLT in Cycle 1, then enrollment to Part B will be suspended pending study committee discussion. If Part A is complete and the initial cohort of 6 adult patients in Part B is deemed safe, up to 19 patients will be enrolled into Stage 1 with a maximum of 12 adult patients. However, if at any point the percentage of patients experiencing a Cycle 1 DLT is >33%, then the study will be suspended pending internal review. This will include DLTs observed for all younger patients from Part A that were assigned to the MTD/RP2D used in Part B of the study.

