Design Characteristics: Each patient enrolled will be evaluated for: (1) complete or partial response as defined by the RECIST criteria where the first evaluation of CR or PR is made at or before the end of the sixth cycle of study therapy (denoted as R below); or (2) stable disease after four months of therapy or at the end of the sixth cycle, whichever occurs first (denoted as S below). We will not be interested in promoting the agent for further investigation if the probability of response in any particular individual is less than or equal to 0.05 ($P(R) \leq 0.05$) and the probability of remaining analytic event free in any particular individual is less than or equal to 0.20 ($P(S) \leq 0.20$). We will be interested in promoting the agent for further investigation if the probability of response in any particular individual is at least 0.22 ($P(R) \geq 0.22$) **or** the probability of remaining analytic event free in any particular individual is at least 0.42 ($P(S) \geq 0.42$).

For the calculations below, it is assumed $\Pr(S | R) = 0.90$.

The statistical characteristics of this design are:

Probability of four month disease control	Probability of RECIST response	Probability of Stopping After Stage 1 (and concluding the drug is ineffective)	Probability of Concluding the Drug is Ineffective at the Conclusion of the Trial	Probability of Concluding the Drug is Effective at the Conclusion of the Trial
0.20	0.05	0.56	0.89	0.11
0.42	0.22	0.014	0.05	0.95
0.42	0.05	0.044	0.096	0.904
0.20	0.22	0.056	0.21	0.79

We will concurrently enroll on the Phase 1 and Phase 2 studies. While the Phase 1 study is accruing we will limit the Phase 2 enrollment to osteosarcoma patients greater than 21 years of age to ensure the completion of the phase 1 portion of this study. After the Phase 1 study is complete, patients less than or equal to 21 will be enrolled into the Phase 2

THIS PROTOCOL IS FOR RESEARCH PURPOSES ONLY, SEE PAGE 1 FOR USAGE POLICY

portion of this study. The Phase 2 study will cap the number of older patients (>21 years) enrolled into Stage 1 at 12 patients to ensure a representative number of patients in both age groups. Without this cap, it may be possible to open Stage 2 of the Phase 2 study without having enrolled any younger patients and stage 2 would have opened based on information collected solely in older patients. Osteosarcoma patients enrolled in Phase 1 will also be included in the Phase 2 part of the study.

11.7 Method of Analysis – Phase 2

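### Osteosarcoma patients pooled from Part A into Part B have, unless they respond, no scheduled scan at the end of cycle 4, so their four-month disease control is read 28 days early or late

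*Combined protocol and SAP*

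**What the plan says.** Section 11.6 pools across the two parts in two places. Its opening counts "Data collected from patients from the dose determining portion (Part A) treated at the MTD/RP2D and who meet eligibility criteria for Part B" in the Phase 2 evaluation. Its closing text is broader: "Osteosarcoma patients enrolled in Phase 1 will also be included in the Phase 2 part of the study".

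The evaluation table in Section 8.1 has two tumor evaluation rows. The general row asks for a scan at the end of cycle 1 and then "Every other cycle x 2 then q 3 cycles". The Part B Phase 2 row asks for scans "After cycles 2,4 and 6 and then q 3 cycles". A footnote to both rows adds a confirmatory scan for responders: "Tumor Disease Evaluation should be obtained on the next consecutive cycle after initial documentation of either a PR or CR".

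Under Section 5.1, "A cycle of therapy is considered to be 28 days". Disease control in Section 11.6 means "stable disease after four months of therapy or at the end of the sixth cycle, whichever occurs first"; Section 11.7 uses the same timing and also counts a complete or partial response. Neither section names the scan that decides, gives a window around it, or moves pooled Part A patients to the Part B row.

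**The concern.** Four-month disease control is part of a primary aim (Section 1.1.5) and one of the two limbs of the go/no-go rule: 5 or more successes among 19 at Stage 1, 9 or more among 29 at the end. The 20% and 42% rates behind that rule presuppose one assessment time for everyone. If some counted patients are scanned on a calendar that skips the end of cycle 4, their status is read earlier or later than the rest. An earlier reading makes success easier, a later one harder. While the choice is open, it could be settled after results are known, and with thresholds this low one reclassified patient can change the decision.

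The matter can recur. Section 2.5 says that Amendment #2A opens the PK expansion to solid-tumor patients up to 21 years of age, and Section 8.1 has no separate scan row for that cohort.

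**Working it through.** **Inputs.** Cycle length 28 days (5.1); scan rows (8.1); null rates 0.20 for disease control (S) and 0.05 for response (R); alternatives 0.42 or 0.22; Pr(S|R) = 0.90; stage rules for 19 and then 10 patients (all 11.6). The number of pooled patients, k, is not given, so it is varied.

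**Step 1: scan days.**
- General row, read as cycles 1, 3 and 5: 1 × 28 = 28, 3 × 28 = 84, 5 × 28 = 140.
- Part B row: 2 × 28 = 56, 4 × 28 = 112, 6 × 28 = 168.
- Against the Part B cycle-4 scan, the nearest Part A scans are 112 − 84 = 28 days early and 140 − 112 = 28 days late.

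The gap affects non-responders. A first response after cycle 3 brings a confirmatory scan after cycle 4.

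**Step 2: reproduce the plan's table.** Each patient falls in one of four cells: S and R, 0.9·P(R); S only, P(S) − 0.9·P(R); R only, 0.1·P(R); neither, the remainder. At the null these are 0.045, 0.155, 0.005 and 0.795. Exact enumeration over 19 and then 10 patients gives:

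| P(S), P(R) | Stop at Stage 1: stated / recomputed | Conclude effective: stated / recomputed |
|---|---|---|
| 0.20, 0.05 | 0.56 / 0.564 | 0.11 / 0.108 |
| 0.42, 0.22 | 0.014 / 0.0135 | 0.95 / 0.949 |
| 0.42, 0.05 | 0.044 / 0.045 | 0.904 / 0.904 |
| 0.20, 0.22 | 0.056 / 0.057 | 0.79 / 0.789 |

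The stated operating characteristics reproduce to within rounding.

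**Step 3: effect of scan time (assumption).** Take a constant progression hazard anchored at the Part B cycle-4 scan: S(t) = S(112)^(t/112).
- Null: 0.20^(84/112) = 0.20^0.75 = 0.299; 0.20^(140/112) = 0.20^1.25 = 0.134.
- Alternative: 0.42^0.75 = 0.522; 0.42^1.25 = 0.338.

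**Step 4: full two-limb rule.** Among the 19 Stage 1 patients, k take the shifted rate; the other 19 − k and the 10 in Stage 2 keep the Day 112 rate. P(R) and Pr(S|R) are unchanged.

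| k | Day 140: false positive | Day 140: power at (0.42, 0.05) | Day 84: false positive | Day 84: power at (0.42, 0.05) |
|---|---|---|---|---|
| 0 | 0.108 | 0.904 | 0.108 | 0.904 |
| 1 | 0.102 | 0.898 | 0.117 | 0.911 |
| 2 | 0.097 | 0.892 | 0.126 | 0.918 |
| 3 | 0.091 | 0.886 | 0.136 | 0.924 |
| 6 | 0.077 | 0.866 | 0.169 | 0.940 |

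**The case against.** A reader might infer that pooling inflates the false-positive rate, since the Day 84 columns reach 0.169. The wording does not support that as the expected result. Disease control is judged after four months, and Day 84 is three 28-day cycles, short of four months on any count. Day 140 is the first scan that qualifies, and it works against the drug. The Day 84 columns show only what happens if a scan the definition excludes were used anyway.

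A reader might also anchor the 20% at calendar four months, about Day 122, and find a larger effect. That mixes two clocks. On that curve Part B's own Day 112 scan reads 0.20^(112/122) = 0.228, so Part B patients would not sit at 20% either.

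Further points on the other side stand:
- Part A takes any non-CNS solid tumor, with measurable or merely evaluable disease (4.1.2, 4.1.3). Only osteosarcoma with measurable disease treated at the RP2D can be pooled. Six such patients is an illustration; the documents give no count.
- Counting PK-expansion patients is not settled. The first pooling sentence refers to the dose determining portion, which read literally leaves them out. The second refers to Phase 1, and Section 11.1 includes the 6 PK patients in the Part A total of 23 (18/0.8 = 22.5, rounded up).
- Clinical progression ends therapy (10.1) and need not be confirmed by imaging (8.1 footnote), and patients lost to follow-up count as failures (11.7). Some patients who progress between scans would therefore be classified without one, which shrinks the effect.
- Cycles 3 and 5 is the natural reading of the general row, but it is not written out.

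None of this supplies a rule linking the two calendars.

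**Conclusion.** The point holds as a mismatch of assessment times within one pooled count. The endpoint is worded identically for everyone and the design table is correct; only the timing differs. Only patients whose disease progresses between Day 84 and Day 140 can be classified differently.

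Followed literally, the plan leads to the Day 140 scan and a modest loss: for 1 to 6 pooled patients, power at (0.42, 0.05) falls by about 0.006 to 0.038 and the false-positive rate falls as well. For one or two patients this is small. The sizes rest on a constant hazard, on 20% or 42% holding at Day 112, on all pooled patients being in Stage 1, and on no progression being found between scans. The change is worth making because it is cheap and closes a choice that could otherwise be made with results in hand.

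**What to change.** 1. Footnote Section 8.1 so that any osteosarcoma patient with measurable disease in Part A or the PK expansion who will be counted in Part B follows the Part B Phase 2 scan row.
2. In 11.6 and 11.7, name the end-of-cycle-4 scan as the deciding scan for all counted patients. For those already enrolled without it, count a success only if the next scheduled scan, at the end of cycle 5, shows at least stable disease. Do not define the deciding scan as the first at or after four months: in calendar months that would send Part B to Day 168 and Part A to Day 140.
3. Reconcile the two pooling sentences in 11.6 as to whether PK-expansion patients are counted.
4. Report the decision with and without the pooled patients.

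The cost is a footnote and a few sentences. The count is slightly conservative for patients already enrolled without the deciding scan. If the end-of-cycle-1 scan is kept, patients moved to the Part B row have one additional scan over six cycles (cycles 1, 2, 4 and 6 against 1, 3 and 5); if it is dropped, there is none.

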12.0 EVALUATION CRITERIA

12.1 Common Terminology Criteria for Adverse Events (CTCAE)

The descriptions and grading scales found in the revised NCI Common Terminology Criteria for Adverse Events (CTCAE) version 5.0 will be utilized for AE reporting. All appropriate treatment areas should have access to a copy of the CTCAE version 5.0. A copy of the CTCAE version 5.0 can be downloaded from the CTEP website (http://ctep.cancer.gov/protocolDevelopment/electronic_applications/ctc.htm).

12.2 Response Criteria for Patients with Solid Tumors

See the table in [section 8.0](#) for the schedule of tumor evaluations. In addition to the scheduled scans, a confirmatory scan should be obtained on the next consecutive cycle following initial documentation of objective response.

Response and progression will be evaluated in this study using the revised Response Evaluation Criteria in Solid Tumors (RECIST) guideline (version 1.1) [*Eur J Ca* 45:228-247, 2009]. Key points are that 5 target lesions are identified and that changes in the *largest* diameter (unidimensional measurement) of the tumor lesions but the *shortest* diameter of malignant lymph nodes are used in the RECIST v 1.1 criteria.

12.2.1 Definitions

- a) Evaluable for objective response: Eligible patients who receive at least one dose of protocol therapy will be considered evaluable for response. Evaluable patients who demonstrate a complete or partial response confirmed by central review before receiving non-protocol anti-cancer therapy will be considered a responder. All other evaluable patients will be considered non-responders.
- b) Evaluable Non-Target Disease Response: Eligible patients who have lesions present at baseline that are evaluable but do not meet the definitions of measurable disease and have received at least one dose of protocol therapy will be considered evaluable for non-target disease. The response assessment is based on the presence, absence, or unequivocal progression of the lesions.

12.2.2 Disease Parameters

- 12.2.2.1 Measurable disease: Measurable lesions are defined as those that can be accurately measured in at least one dimension (longest diameter to be recorded) as ≥ 20 mm by chest x-ray, as ≥ 10 mm with CT scan, or ≥ 10 mm with calipers by clinical exam. All tumor measurements must be recorded in millimeters (or decimal fractions of centimeters).

Note: Tumor lesions that are situated in a previously irradiated area might or might not be considered measurable. If the investigator thinks it appropriate to include them, the conditions under which such lesions should be considered must be defined in the protocol.

12.2.2.2 Malignant lymph nodes: To be considered pathologically enlarged and measurable, a lymph node must be ≥ 15 mm in short axis when assessed by CT scan (CT scan slice thickness no greater than 5 mm). At baseline and in follow-up, only the short axis will be measured and followed.

12.2.2.3 Non-measurable disease: All other lesions (or sites of disease), including small lesions (longest diameter < 10 mm or pathological lymph nodes with ≥ 10 to < 15 mm short axis), are considered non-measurable disease. Bone lesions, leptomeningeal disease, ascites, pleural/pericardial effusions, lymphangitis cutis/pulmonitis, inflammatory breast disease, and abdominal masses (not followed by CT or MRI), are considered as non-measurable.

Note: Cystic lesions that meet the criteria for radiographically defined simple cysts should not be considered as malignant lesions (neither measurable nor non-measurable) since they are, by definition, simple cysts. 'Cystic lesions' thought to represent cystic metastases can be considered as measurable lesions, if they meet the definition of measurability described above. However, if non-cystic lesions are present in the same patient, these are preferred for selection as target lesions.

12.2.2.4 Target lesions: All measurable lesions up to a maximum of 2 lesions per organ and 5 lesions in total, representative of all involved organs, should be identified as target lesions and recorded and measured at baseline. Target lesions should be selected on the basis of their size (lesions with the longest diameter), be representative of all involved organs, but in addition should be those that lend themselves to reproducible repeated measurements. It may be the case that, on occasion, the largest lesion does not lend itself to reproducible measurement in which circumstance the next largest lesion that can be measured reproducibly should be selected. A sum of the diameters (longest for non-nodal lesions, short axis for nodal lesions) for all target lesions will be calculated and reported as the baseline sum diameters. If lymph nodes are to be included in the sum, then only the short axis is added into the sum. The baseline sum diameters will be used as reference to further characterize any objective tumor regression in the measurable dimension of the disease.

12.2.2.5 Non-target lesions: All other lesions (or sites of disease) including any measurable lesions over and above the 5 target lesions should be identified as non-target lesions and should also be recorded at baseline. Measurements of these lesions are not required, but the presence, absence, or in rare cases unequivocal progression of each should be noted throughout follow-up.

